8.6. Investigational Product Compliance

Accurate recording of all IP administration (including dispensing and dosing) will be made in the appropriate section of the subject's eCRF and in the source documents.

8.7. Blinding

With the exception of individuals noted below, all study site personnel, subjects, and sponsor personnel and their designees involved with the study, including the sponsor medical monitor will remain blinded to treatment assignment until the last subject has completed Month 6 and all relevant study data have been processed and integrated into the clinical database and the data base is locked. At that time the sponsor and their designees will be unblinded. Study site personnel and subjects will remain blinded during the course of the study. The personnel in the Clinical Supply Management Group responsible for shipping IP and Global Drug Safety personnel will be unblinded. A scientist outside of the study team will be unblinded to assess the data on biomarkers. The following personnel external to the sponsor will also be unblinded to treatment assignment: the pharmacist, or designee responsible for mixing/ thawing IP, at each study site and the IVRS group. Members of the external DMC will have access to unblinded data as specified in Section 6.5.1.

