4.1. Study Design

This is a Phase 2, randomized, double-blind, placebo-controlled, dose range finding study in subjects who have DPN. The study will enroll approximately 24 subjects. Subjects will be randomized to receive one of 3 treatments: PDA-002 (3×10^6 cells), PDA-002 (30×10^6 cells), or placebo (vehicle control) in a 1:1:1 randomization approach. Investigational product or placebo will be administered monthly (3 administrations total on Study Days 1, 29, and 57). Subjects will be treated and evaluated as indicated in the Table of Events (Table 1).

Subjects will undergo a Screening Period (up to 28 days in duration) to determine study eligibility and baseline levels of signs and symptoms of DPN will be established. Subjects will then enter a Treatment Period (6 months in duration). During the Treatment Period, subjects will be evaluated on an ongoing basis (at 8 scheduled study visits). Subjects will receive IM injections of IP on Study Days 1, 29, and 57 as fifteen 0.30 mL injections (below the knee and above the ankle) in one lower extremity in a blinded manner. After completing the Treatment Period, subjects will enter the Follow-up Period where they will continue to be evaluated at scheduled study visits over the subsequent months.

An analysis of all study data will occur after the last subject has completed Visit 9 (Month 6) and after the last scheduled study visit. Analyses to be performed can be found in the Statistical Analysis Plan.

The study will be subject to oversight by an independent Data Monitoring Committee (DMC). The DMC will review unblinded efficacy and safety data on an ongoing basis (both scheduled and ad hoc [if needed]) as outlined in the DMC Charter.

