6.3. Follow-Up Period

All subjects will be followed for 28 days after the last dose of IP for AE reporting, as well as SAEs that will be followed until the last study visit and made known to the investigator at any time thereafter that are suspected of being related to IP, as described in Section 11.1.

The Follow-up Period will take place from Visit 10 through Visit 13 and include Early Termination. Visits should occur on the day specified ± 3 days or ± 7 days as specified in the Table of Events (Table 1).

All other procedures (as discussed in Section 6.1 and Section 6.2) will be conducted as per the Table of Events (Table 1).

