10.2. Study Population Definitions

The following analysis populations are planned for this study:

Screening Population (Screen): The Screening Population includes all subjects who provide informed consent and screen for eligibility during the Screening Period (Day -28 to Day -1).

Safety Population (Safety): The Safety Population includes all subjects who receive any amount of IP.

Modified Intent To Treat (mITT): The mITT population includes all subjects who receive any amount of IP and subsequently provide at least one efficacy assessment.

Other study populations or subgroup populations may be identified during the course of this study. Any additional study populations or subgroups will be clearly identified either in the SAP or, if after database lock, then as post-hoc study populations in the clinical study report.

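### The Month 6 lock unblinds the sponsor and its designees, medical monitor included, with no firewall, while blinded sites still have Month 12 exploratory ratings and late safety data to collect

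*Combined protocol and SAP*

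**What the plan says.** Section 8.7 (Blinding) sets one rule, with listed exceptions, for site staff, subjects, sponsor staff and designees. All of them, "including the sponsor medical monitor will remain blinded to treatment assignment until the last subject has completed Month 6", and until the relevant data "have been processed and integrated into the clinical database and the data base is locked". After that the two sides part:

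- Sponsor side: "At that time the sponsor and their designees will be unblinded".
- Site side: "Study site personnel and subjects will remain blinded during the course of the study".

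Some people are unblinded earlier, by named role. On the sponsor side: "The personnel in the Clinical Supply Management Group responsible for shipping IP and Global Drug Safety personnel will be unblinded". A scientist outside the study team is unblinded for biomarker data. Outside the sponsor, the site pharmacist or designee, the IVRS group and the DMC have access.

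The study continues after Month 6. Section 6.3 says: "The Follow-up Period will take place from Visit 10 through Visit 13 and include Early Termination". Table 1 places those visits at Months 8, 10, 12 and 14. Section 4.1 schedules an analysis of all study data once the last subject has "completed Visit 9 (Month 6) and after the last scheduled study visit", so there are two analyses. Section 10.8 calls the first an interim analysis.

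Section 10.2 allows further populations or subgroups to be identified while the study is running. They are to be set out in the SAP or, "if after database lock, then as post-hoc study populations in the clinical study report". It does not say which lock is meant. Section 10.1 places the detailed SAP in a separate document and gives no date for finalising it.

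**The concern.** The unblinding rule is written for an organisation, not for roles. Several of the people it covers deal with blinded sites under other sections:

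- Investigators may consult the medical monitor before discontinuing a subject (8.2.1, 12.1.3). They are asked to try hard to reach the monitor before breaking the blind (13.2).
- Sponsor representatives visit sites, check source data and go through discrepancies with the investigator and staff (16.1).
- Data discrepancies are raised with the clinical team and, where needed, with site staff (15.2).
- Causality is to be reassessed as information arrives (11.2.3), so a blinded judgement can stay open after the lock.

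Someone who knows a subject's assignment can give it away without meaning to. Examiner-scored and self-reported scales are the measurements most open to that. With 8 subjects per arm at about 5 sites, one or two disclosures could matter to the longer-term comparison, which Section 4.3 gives as one purpose of follow-up.

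The second strand is the wording of 10.2. If the undefined lock were a later, final one, a population added to the SAP after the Month 6 results were known would not be labelled post hoc.

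**Working it through.** The plan states no figure on this point. The check is to establish what remains to be collected after the lock, and then how many subjects that could involve.

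**What remains after Month 6 (Table 1)**

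| Visit | Scheduled content relevant here |
|---|---|
| Months 8 and 10 | Examination and vital signs, medication, adverse events |
| Month 12 | NTSS-6, UENS, NIS-LL, PGICN, Norfolk QOL-DN; also nerve conduction, QSART, hyperspectral imaging, vascular reactivity; retinal examination, HbA1c, adverse events |
| Month 14 | Examination and vital signs, laboratory tests, medication, adverse events |

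No skin biopsy is scheduled after Month 6, so the ENFD primary endpoint (3.1) is complete for every subject at the lock. The scales have one scheduled time point after it, Month 12. The Early Termination column also lists them, so a subject who leaves during follow-up could be rated then. For the last subject enrolled, the time left after Month 6 is Day 425 − Day 186 = 239 days, with four visits.

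**How many subjects reach Month 12 after unblinding**

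Two inputs are not in the documents and are assumed: enrolment is uniform over E months, and the lock comes L months after the last subject's Month 6 visit.

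- Lock time from first enrolment: E + 6 + L.
- A subject enrolled at time t has Month 12 at t + 12. This falls after the lock if t > E − (6 − L).
- Share exposed = min(1, (6 − L)/E), for L up to 6.

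| Lag L | E = 6 months | E = 12 months |
|---|---|---|
| 2 months | 4/6 × 24 = 16 | 4/12 × 24 = 8 |
| 4 months | 2/6 × 24 = 8 | 2/12 × 24 = 4 |
| 6 months | 0 | 0 |

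The same reasoning for Month 14 gives min(1, (8 − L)/E). At L = 2 that is 24 of 24 for E = 6 and 12 of 24 for E = 12. Those visits carry safety data but none of the scales.

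**Which lock Section 10.2 means**

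The only lock whose timing the protocol defines is the Month 6 lock in 8.7, the event that triggers unblinding. If 10.2 means that one, every population defined after the look is already post hoc. The second analysis in 4.1 implies a later lock. If 10.2 means that one, there is an interval between the two in which an addition would escape the label. The text supports the first reading at least as well as the second and settles neither.

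**The case against.** The case for leaving the plan alone has real weight.

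- **Nothing decisive is exposed.** The primary endpoint is closed at the lock. The Month 12 measures are exploratory and analysed descriptively (10.6), in a study meant to inform the next one (10.3). This stands and limits the importance of the point.
- **Early unblinding has a purpose.** The Month 6 results serve a proof-of-concept decision (10.6). This also stands, but the decision does not need site-facing staff to hold subject-level assignments.
- **The leak routes are possible, not shown.** The last dose is on Day 57, so no treatment decision remains at the lock. Section 8.2.1 says contact with the medical monitor is not required. Section 8.7 does not name site monitors as designees. Nothing describes the sponsor advising raters on scoring. For self-reported scales, knowledge would have to pass from sponsor to site to subject. All this is fair. What remains is that contact is provided for (13.2, 15.2, 16.1) and nothing separates it from the treatment codes.
- **Part of the safety channel is open already.** Global Drug Safety is unblinded throughout. Section 11.5.1 has SAE queries coming from the sponsor's drug safety group, which may be the same people. A change to the Month 6 rule would not alter that.
- **The late safety data may be narrower than they look.** Table 1 and Section 6.3 limit adverse event follow-up to 28 days after the last dose, with SAEs to the last visit. Section 11.1 records all adverse events to the last visit. These need reconciling. SAEs remain exposed on either reading.

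A reader might infer from 10.2 that populations chosen after seeing the Month 6 results may be presented as pre-planned. The documents do not support that: 10.2 expressly labels populations identified after database lock as post hoc, and the only lock given a time is the Month 6 one. The defect is that the lock is unnamed.

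**Conclusion.** The point holds in a limited form. Section 8.7 unblinds the sponsor and its designees at the Month 6 lock, with the medical monitor expressly in that group, no role held back and no firewall, while blinded sites continue follow-up. At risk are the Month 12 exploratory ratings and late safety data, for subjects not yet through those visits.

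The size depends on two assumed quantities. Over the cases worked, between 0 and 16 of 24 subjects would have Month 12 after unblinding. These are counts of visits open to bias, not estimates of bias.

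Two wider conclusions might be drawn and should not be. The primary result is not threatened. Nor are subjective ratings exposed through to Month 14: after Month 6 they are scheduled at Month 12 only, so the Month 14 counts concern safety data alone.

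On populations, the finding is an ambiguity that one sentence would remove.

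**What to change.** 1. **Section 8.7.** Limit the Month 6 unblinding to a named analysis and decision group with no site contact. State that the medical monitor, site monitors and data managers who query sites stay blinded to subject-level assignment until the final lock. The section already unblinds some staff by named role, so this follows its own pattern.
2. **Section 10.2.** State that database lock there means the Month 6 lock, so that any population or subgroup defined after the Month 6 unblinding is reported as post hoc. Finalise the SAP and its populations before that unblinding.

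The cost is protocol and blinding-plan wording. The downside is small: these existing roles stay blinded for about 8 more months (Month 14 minus Month 6 for the last subject, if both locks take equally long). The timing and content of the Month 6 analysis do not change.

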9. CONCOMITANT MEDICATIONS AND PROCEDURES

9.1. Permitted Concomitant Medications and Procedures

Concomitant medications and procedures for treatment of DPN are allowed; however, subjects should maintain stable doses and stable dose regimens of neuropathy medications (such as anticonvulsants like pregabalin, gabapentin, and antidepressant medications such as duloxetine) for at least 2 months prior to the initial dose of IP.

An effort should be made to maintain the subject's standard medical care through the Treatment Period (through Visit 9) unless changes are necessary to ensure the best care for the subject.

9.2. Prohibited Concomitant Medications and Procedures

It is recommended that subjects continue to maintain stable doses /dose regimens of DPN therapies through the Treatment Period (Study Visit 9) whenever possible.

9.3. Required Concomitant Medications and Procedures

Subjects should receive standard of care prior to and throughout the study.

10. STATISTICAL ANALYSES

10.1. Overview

The primary objective of the study is to assess efficacy of PDA-002 in subjects with DPN as measured by the change in epidermal nerve histology at 6 months following IM administration of 2 different doses of PDA-002 or placebo. Assessment of epidermal nerve histology will be quantified using an immunohistochemical technique to determine ENFD.

The secondary objective of the study is to assess the safety and tolerability of IM administration of 2 different doses of PDA-002 or placebo in subjects with DPN. Safety will be assessed by the type, frequency, severity, and potential relationship of adverse events to treatment with IP.

A detailed Statistical Analysis Plan (SAP) will be provided in a separate document. Exploratory biomarker analysis and other experimental evaluations will be outlined in separate documents and will not be included as part of the Clinical Study Report.

10.2. Study Population Definitions

The following analysis populations are planned for this study:

Screening Population (Screen): The Screening Population includes all subjects who provide informed consent and screen for eligibility during the Screening Period (Day -28 to Day -1).

Safety Population (Safety): The Safety Population includes all subjects who receive any amount of IP.

Modified Intent To Treat (mITT): The mITT population includes all subjects who receive any amount of IP and subsequently provide at least one efficacy assessment.

Other study populations or subgroup populations may be identified during the course of this study. Any additional study populations or subgroups will be clearly identified either in the SAP or, if after database lock, then as post-hoc study populations in the clinical study report.

10.3. Sample Size and Power Considerations

The sample size of 24 subjects total, 8 per treatment arm, was selected in order to provide preliminary safety and efficacy information in a randomized, double-blind fashion. The study is designed to provide an estimation of the treatment effect of active therapy and placebo to plan a sample size for the next study.

Based upon a previous study evaluating the therapeutic effect of a combination of L-methylfolate, methylcobalamine, and pyridoxal 5 phosphate in subjects with DPN (Jacobs, 2011), the mean ENFD was 1.56 fibers/mm at baseline and 3.07 fibers/mm after 6 months of treatment with a standard deviation of 1.5 fibers/mm for the mean increase. Assuming the same treatment effect is observed from baseline, the sample size of 16 subjects actively on therapy resulting from combining the 2 active arms has a 96% power to detect a similar mean change at 6 months from baseline, with a two-sided test and a Type I error rate set at 0.05. Assuming the subjects treated with placebo would not have a change from baseline, the study has

60% power to detect similar differences between placebo and active therapy with PDA-002, with a two-sided test and a Type I error rate set at 0.05.

10.4. Background and Demographic Characteristics

Baseline and demographic characteristic will be summarized by treatment arm. Subjects' age, height, weight, and baseline characteristics will be summarized using descriptive statistics, while gender, race and other categorical variables will be provided using frequency tabulations. Medical history data will be summarized using frequency tabulations by system organ class and preferred term.

10.5. Subject Disposition

Subject disposition (analysis population allocation, entered, discontinued, along with primary reason for discontinuation) will be summarized using frequency and percentage for both treatment and follow-up phases. A summary of subjects enrolled by site will be provided. Protocol deviations will be summarized using frequency tabulations.

10.6. Efficacy Analysis

The planned analyses will be fully described in a comprehensive SAP.

The primary efficacy analysis will be an evaluation of change from baseline in ENFD at 6 months following treatment with either dose of PDA-002 or placebo. Results will be used to assess the proof of concept for further study of PDA-002 in subjects with DPN. The analyses will also take into account the possible inter-subject variability of measurements evaluated in both the treated leg (with active or placebo) and the other leg that received placebo.

Changes in the various exploratory efficacy endpoints including within subject differences between left and right leg measurements will be evaluated using descriptive statistics.

In general, exploratory endpoints that are categorical will be examined using descriptive summaries such as counts and percentages, whereas exploratory endpoints that are continuous will be examined using means, standard deviations and medians. The results of the exploratory analyses will allow for better definition of the clinical efficacy endpoints.

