Immunological/Inflammation Assessments

Immunological/inflammation assessment will include the following testing:

• Anti-HLA antibodies as indicated in the Table of Events (Table 1).

Hemoglobin A1c

Hemoglobin A1c will be measured as indicated in the Table of Events (Table 1).

Coagulation Tests

Coagulation tests including assessment of PT/PTT, D-dimers, fibrinogen, and platelets will be assessed as indicated in the Table of Events (Table 1) prior to dosing with IP and approximately 2 hours post-dose. Assessments can be performed within 1 hour of the 2 hour post dose time frame.

Tryptase and Histamine

Tryptase and histamine levels will be assessed on the day of treatment prior to dosing with IP and approximately 2 hours postdose as indicated in the Table of Events (Table 1).

Exploratory Biomarkers

Exploratory biomarkers will be measured as indicated in the Table of Events (Table 1).

Skin Biopsies: Two 3mm thickness skin punch biopsies will be taken at the lateral aspect of the distal legs (2 biopsies; 1 per leg) approximately 10 cm above the lateral malleolus, and two biopsies will be taken at the volar aspect of the forearm (2 biopsies on 1 forearm). Instructions for tissue collection, handling, and shipping instructions are located in the Laboratory Manual.

Contraception: Females of childbearing potential¹ must use adequate contraception for the duration of their participation in the study (which includes 28 days prior to starting IP, during the Treatment Period [including dose interruptions], and during the Follow-up Period). Adequate contraception is defined as the simultaneous use of 2 of the following forms of contraception methods: oral, injectable or implantable hormonal contraception; tubal ligation; intrauterine device (IUD); barrier contraceptive with spermicide; or a vasectomized partner.

Males (including those who have had a vasectomy) must agree to use barrier contraception (latex condoms) when engaging in sexual activity with females of child bearing potential (FCBP) for the duration of their participation in the study, including the Follow-up Period.

Retinal Assessment: Retinal assessment conducted by an ophthalmologist or optometrist will be performed and scored using the International Clinical Diabetic Retinopathy Disease Severity Scale (Appendix B). Results will be recorded in the eCRF and in the source documents.

6-Item Neuropathy Total Symptom Score (NTSS-6): To be completed as outlined in Efficacy Procedures Section 6.4.

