8.2. Treatment Administration and Schedule

Investigational product (IP) will be administered on Study Days 1, 29 and 57. Thawing of the IP should not begin until it is confirmed that the subject meets the inclusion/exclusion criteria. Investigational product thawing will be performed by qualified site personnel according to the instructions in Appendix E. Three 3 mL syringes will each be filled with 1.5 mL of IP, and then capped. Syringes will be masked to preserve blinding, and transferred to the personnel administering the injections.

Subjects will receive IP administered as fifteen 0.30 mL injections (approximately 4.5 mL total) in one leg. The target region is suggested to be below the knee and above the ankle. Injections are suggested to be at least 1 cm apart horizontally and laterally and at a depth of approximately 1 to 4 cm. It is suggested that they be administered in a pattern of 3 x 5 injections around the leg, and injections should not be near a blood vessel. The administrator will be blinded to treatment.

PDA-002 is not intended for intravenous administration. When the injection is given, the syringe should be aspirated to avoid inadvertent venous administration. If any blood is aspirated into the syringe, the needle is to be pulled out a little, and the syringe re-aspirated. If no blood is seen, the IP may be injected.

Vital signs (including heart rate, respiration, blood pressure, body temperature) will be monitored prior to starting the injections and at 1 and 2 hours (\pm 15 minutes) after completion of

the injections. Blood samples for tryptase and histamine, coagulation assessments, and exploratory biomarkers will be collected as indicated in the Table of Events (Table 1).

The investigational centers must also offer appropriate supplemental services that support clinical care to ensure that the protocol specified IP administration and monitoring will be followed.

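### Section 10.6 names no baseline adjustment and no primary leg for the ENFD comparison with placebo; ANCOVA on baseline would cost little and, under assumed correlations, change the stated 60% power by about -2 to +16 points

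*Combined protocol and SAP*

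**What the plan says.** Section 10.6 gives the primary analysis as follows: "The primary efficacy analysis will be an evaluation of change from baseline in ENFD at 6 months following treatment with either dose". No statistical test, contrast or covariate follows. The one analytic feature mentioned is variability of measurements in "both the treated leg (with active or placebo) and the other leg that received placebo".

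Section 10.1 defers the method: "A detailed Statistical Analysis Plan (SAP) will be provided in a separate document". Section 10.6 does the same. That document is not in the file.

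Section 10.3 combines the two active arms (16 subjects) and claims 96% power for the change from baseline within them and "60% power to detect similar differences between placebo and active therapy with PDA-002". It also gives the trial's purpose: it is "designed to provide an estimation of the treatment effect of active therapy and placebo to plan a sample size for the next study".

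On the legs, section 4.1 has the product injected "below the knee and above the ankle) in one lower extremity in a blinded manner", and section 8.2 has it given as "fifteen 0.30 mL injections (approximately 4.5 mL total) in one leg". Section 6.1 places the leg biopsies at each visit on both sides ("2 biopsies; 1 per leg) approximately 10 cm above the lateral malleolus"), and section 6.4 also takes the ENFD specimens bilaterally.

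**The concern.** Two things are left open in the protocol text.

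The first is the model. The only guide to the comparison with placebo is the power figure, which corresponds to an unadjusted comparison of change scores. Baseline ENFD is measured at screening in every subject. With only 8 placebo subjects, the groups can easily differ at baseline by chance. A change-score difference carries part of that imbalance into the estimate, whereas ANCOVA on baseline takes it out. The estimate serves as proof of concept (10.6) and sizes the next study (10.3), so its precision matters.

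The second is the variable. Each subject yields two leg ENFD values per biopsy visit, and no section says which one, or which combination, is primary. The description of the second leg in 10.6 does not agree with 4.1 and 8.2. Until it does, the status of that leg is unclear, and so is the ENFD value to be analysed.

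Under section 8.7 the sponsor is unblinded once the Month 6 database is locked. A model or leg chosen after that could be chosen with the results in view.

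**Working it through.** **Inputs from section 10.3.** Effect 3.07 - 1.56 = 1.51 fibers/mm; SD of change 1.5; placebo change 0; 16 active (two arms pooled) v 8 placebo; two-sided 0.05.

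**The plan's own figures**

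- Against placebo, unadjusted: standard error = 1.5 x sqrt(1/16 + 1/8) = 0.650. Noncentrality = 1.51/0.650 = 2.32, with 22 df and critical t 2.074. Power is **60.4%** (stated 60%). The 95% CI half-width is 2.074 x 0.650 = 1.35 fibers/mm.
- Within the pooled active arms, one-sample t, n = 16: noncentrality = 1.51/(1.5/4) = 4.03. Power is **96.4%** (stated 96%).
- Variants that do not give 60%: normal approximation 64.2%; one-sided t 72.8%; one dose v placebo (8 v 8) 46.6%.

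Both stated figures therefore stand, and the 60% is that of an unadjusted change-score test.

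**With baseline adjustment.** The documents give neither the baseline to Month 6 correlation (rho) nor the two SDs. They are assumed here: rho 0.3-0.9 and Month 6 to baseline SD ratio k = 1-1.5, with the SD of change held at 1.5.

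- Baseline SD: s0 = 1.5/sqrt(1 + k² - 2 x rho x k)
- Residual SD after adjustment: k x s0 x sqrt(1 - rho²)
- Slope of Month 6 on baseline: k x rho
- Power: noncentral t with 21 df and variance multiplied by 1 + 1/20 = 1.05 for estimating the slope

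Example, k = 1 and rho = 0.3: s0 = 1.5/sqrt(1.4) = 1.27; residual SD = 1.27 x sqrt(0.91) = 1.21; noncentrality = 1.51/(1.21 x sqrt(0.1875 x 1.05)) = 2.81; power 76.5%.

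| k | rho 0.3 | rho 0.5 | rho 0.7 | rho 0.9 |
|---|---|---|---|---|
| 1 | 76.5% | 70.5% | 65.1% | 60.3% |
| 1.25 | 68.6% | 62.9% | 58.9% | 60.3% |
| 1.5 | 64.0% | 59.6% | 58.2% | 68.9% |

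Simulation agrees to within about 0.5 point (for example 76.9% in the first cell and 58.1% in the lowest). Against 60.4%, the change runs from about -2 to +16 points. Seven cells gain. Five do not: k = 1 with rho 0.9; k = 1.25 with rho 0.7 and 0.9; k = 1.5 with rho 0.5 and 0.7. In all five the slope lies between 0.75 and 1.125.

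The limits of the adjustment are these. At slope 1 the residual SD stays at 1.5 and power is 58.1%, the worst case. At rho = 0 with equal SDs it is about 86%, so 77% is not a ceiling.

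**Non-normal data.** With skewed, non-negative (gamma) ENFD in the seven cells whose baseline SD is below the 1.56 mean, simulated power was 67-78% for ANCOVA and 62-68% unadjusted. ANCOVA type I error was 4.2-4.7%.

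**Chance imbalance.** A baseline difference D moves the change-score estimate by (slope - 1) x D. One standard error of D is s0 x sqrt(1/16 + 1/8). For k = 1, rho = 0.3 the shift is 0.7 x 1.27 x 0.433 = 0.38 fibers/mm, or 25% of 1.51. For k = 1.5, rho = 0.7 it is 0.05 x 1.40 x 0.433 = 0.03, or 2%. This is the precision gain seen in a single trial; it does not add to the power gain above.

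**The leg passages.** Section 10.6 gives the second leg a placebo. Sections 4.1 and 8.2 give all fifteen injections to one leg and mention none for the other. Sections 6.1 and 6.4 biopsy both. No section selects or combines the two ENFD values.

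**The case against.** The strongest objection is that the model has been deferred, which differs from omitting it. Section 10.6 is a summary, a separate SAP may already specify ANCOVA, and nothing in the wording rules it out: with baseline as a covariate, modelling change or modelling the Month 6 value gives the same treatment difference. An unadjusted power calculation does not commit the analysis to an unadjusted test. All of this stands, and it limits the point to the protocol text.

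Next, the benefit rests on a correlation and SDs that the documents do not give, and its range includes no gain and a small loss. This also stands.

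A reader might further infer that the change-score comparison is biased. It is not: under randomisation it is unbiased, and chance baseline imbalance is already in its standard error. A reader might infer that the 60% is an error or that 77% is available for the asking. The first is refuted by reproducing the figure; the second holds only in the most favourable grid cell.

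Finally, pooling the doses as the primary contrast is not stated in 10.6, and the trial is described as dose range finding. Pooling is nevertheless the contrast on which 10.3 computes its power, and section 2.1 sets PDA-002 against placebo without separating the doses.

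None of these objections touches the leg contradiction, which needs no assumption.

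**Conclusion.** The point holds in limited form. The protocol text leaves the primary ENFD comparison without a baseline adjustment, although the covariate is already collected. Adjustment would give about 58-77% power where the unadjusted test gives 60%, assuming rho 0.3-0.9, an SD ratio of 1-1.5, an SD of change of 1.5, normal data, pooled doses and a common slope across arms. Seven of 12 assumed combinations gain and five do not. The case for adjustment is better precision, with chance imbalance removed from the estimate, at small risk. The documents do not support calling the stated power wrong, the change-score analysis biased, or an unadjusted test prescribed.

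The leg question is certain on the text: the passages disagree and the primary ENFD variable is not uniquely defined. The documents do not settle whether the second leg is injected, and this review takes no position on that.

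**What to change.** 1. In section 10.6, state the primary comparison as ANCOVA of Month 6 ENFD (equivalently, of change) adjusted for baseline ENFD, pooled PDA-002 versus placebo, two-sided 0.05, reported as an adjusted difference with 95% CI. Report each dose versus placebo in the same way as an estimate; unadjusted, 8 v 8 has only about 47% power. Keep within-arm changes descriptive. If the separate SAP already says this, carry it into 10.6; if not, add it to both.
2. Reconcile the account of the second leg in 10.6 with 4.1 and 8.2. Then state which leg's ENFD, or which combination, is the primary variable.
3. Complete both before the Month 6 database lock and unblinding.
4. Optionally, label the 96% in 10.3 as a within-group figure.

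The cost is wording in the protocol and SAP, one degree of freedom, a common-slope assumption, and up to about 2 points of power if the slope of Month 6 on baseline is near 1. No new data or visits are needed.
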